1.0 Objectives

1.1 Describe the purpose, specific aims, or objectives of this research.

Response: To study the effects of liraglutide (a drug used to treat type 2 diabetes) on glucose (sugar) control over the 26 week study period when used in addition to insulin. The use of Liraglutide in Type 1 Diabetes is investigational

1.2 Describe the purpose, specific aims, or objectives.

Response:

Aim 1.1: To compare the mean HbA1c, fasting glucose, weekly glucose, the standard deviation of weekly blood glucose concentrations as recorded by continuous glucose monitoring, fructosamine and the dose of insulin required prior to and following 26 weeks of treatment with liraglutide.

Aim 1.2: To compare the postprandial glucose concentrations following a test meal before and after 26 weeks of treatment with liraglutide.

Aim 2.1: To compare the basal and postprandial glucagon and C-peptide concentrations following a test meal before and after 26 weeks of treatment with liraglutide.

Aim 3.1: To compare ROS generation, TBARS, intranuclear NF κ B binding in MNC, the expression of TLR-4, TNF α , I κ B α , MMP-9, SOCS-3, PKC β II, PTP-1B, GSK-3 β , IKK β , JNK-1, I κ B and pI κ B in MNC and adipose tissue and plasma concentrations of CRP, MCP-1, PAI-1, TNF α , RANTES, free fatty acids (FFA) prior to and following: a) a single injection of liraglutide 1.2mg at first study visit; b) treatment with liraglutide for 26 weeks.

Aim 3.2: To compare the changes in NF κ B binding and the expression of TLR-4, TNF α , I κ B α , SOCS-3, PTP-1B, PKC β II, IKK β and JNK-1 in MNC following a standard meal challenge prior to and after 26 weeks of treatment with liraglutide..

Aim 4.1: To assess subcutaneous fat mass, hepatic fat content and visceral fat mass by MRI of abdomen and DEXA before and 26 weeks after treatment with liraglutide.

Aim 4.2: To assess change in waist circumference, blood pressure, triglycerides, HDL cholesterol and incidence of metabolic syndrome after treatment with liraglutide

Aim 5.1: To compare the gastric emptying as measured by acetaminophen absorption before and 26 weeks after treatment with daily subcutaneous liraglutide injection.

Aim 6.1: To compare the blood pressure using a 24 hour blood pressure monitor before and 26 weeks after treatment with liraglutide.

Aim 6.2: To compare endothelial function by measuring flow mediated dilatation (FMD) in brachial artery before and 26 weeks after treatment with liraglutide.

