Aim 7.1: To compare the quality of life questionnaire scores and depression questionnaire scores before and 26 weeks after treatment with liraglutide

1.3 State the hypotheses to be tested, if applicable.

NOTE: A hypothesis is a specific, testable prediction about what you expect to happen in your study that corresponds with your above listed objectives.

Response:

Hypothesis 1: Treatment with Liraglutide in overweight or obese patients with type 1 diabetes decreases fasting, postprandial and the overall mean glucose concentrations while decreasing the dose of insulin required.

Hypothesis 2: Treatment with Liraglutide decreases basal and postprandial glucagon concentrations and increases basal and postprandial C-peptide concentrations.

Hypothesis 3. Treatment with liraglutide suppresses indices of oxidative and inflammatory stress including the mediators of insulin resistance, in peripheral blood mononuclear cells (MNC), plasma and adipose tissue.

Hypothesis 4: Treatment with liraglutide reduces abdominal adiposity, hepatic and visceral fat mass and improves features of metabolic syndrome.

Hypothesis 5: Treatment with Liraglutide in obese patients with type 1 diabetes delays gastric emptying.

Hypothesis 6: Treatment with Liraglutide in obese patients with type 1 diabetes improves blood pressure and endothelial function.

Hypothesis 7: Treatment with Liraglutide in obese patients with type 1 diabetes improves quality of life and depression as measured by questionnaires.

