1. This will be the first prospectively randomized controlled study to investigate the effect of liraglutide on glycemic levels and variability in overweight and obese type 1 diabetes treated with insulin alone. Liraglutide is the preferred agent for this study since its pharmacokinetics and pharmacodynamics ensure a duration of action of 24 hours. Hitherto, the treatment of type 1 diabetes is based on insulin replacement with novel analogs with appropriate pharmacodynamic profiles or with unique insulin delivery systems. The concomitant use of metformin or pramlintide helps in some patients but the benefits are far from consistent and, therefore, these agents have not made an impact on the treatment of this condition(6).
2. This will be the first study to investigate the role of glucagon and the potential basal and postprandial suppression of glucagon by liraglutide in the pathogenesis and control of glycemia in type 1 diabetics. This is particularly important since in the absence of insulin secretion from the β -cell, there is no paracrine inhibition of glucagon secretion by the α -cell. GLP-1 analogs are known to suppress glucagon(5).
3. With the use of CGM, this study will determine the rapidity of response by liraglutide, which in our preliminary study was observed within the first two days such that we advised patients to reduce their insulin doses by 25% in advance.
4. This will be the first study to attempt to reduce body weight and other features of the metabolic syndrome, while improving glycemic control with addition of a single therapeutic agent in overweight and obese patients with type 1 diabetes. This is particularly relevant since insulin induces weight gain and 40-50% of type 1 diabetics in the US have the metabolic syndrome(14). Liraglutide and the only other licensed drug in this class, exenatide, have been shown not only to reduce body weight but also

to reduce systolic blood pressure plasma triglyceride and CRP concentrations in subjects with type 2 diabetes(8; 9; 15; 16; 18).

- Finally, it will allow us to assess whether liraglutide can activate the dormant β -cells which are known to survive in type 1 diabetics for a long time (19). An analysis in a subset of the study patients with detectable C-peptide will be carried out separately. This will assess the effect of liraglutide in preserving β -cells and the effect of residual β -cell function on the action of liraglutide

Liraglutide treatment in patients with type 1 diabetes

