Study visit day -7: Meal challenge test: In order to assess the changes induced by liraglutide, a meal challenge will be carried out prior to and following liraglutide (week 0 and week 26): a 910 calorie high fat high carbohydrate meal will be given, as in several of our previous papers(20).Bolus dose will be given at 3-4 hours after the ingestion of the meal based on the blood sugar and correction factor for each individual subject as giving bolus insulin immediately before meal may confound the true effects of liraglutide. Acetaminophen (1000 mg for body weight <125lbs, 1250 mg for body weight 125-150 lbs, 1500 mg for body weight 151-175 lbs and 1750 mg for body weight >175 lbs) will be ingested at the beginning of the meal, and the blood levels of acetaminophen will be determined at intervals for assessment of the rate of gastric emptying. Liraglutide will be injected only at week 26 (45 min prior to the meal). Sequential blood samples will be obtained at 0, 15, 30, 45, 60, 90, 120, 150, 180, 210, 240 and 300 min. Samples at 15, 30, 45, 90, 150 and 210 min will be 5 ml while those at 0, 60, 120, 180, 240 and 300 min will be 30 ml (total volume=210 ml). Blood will be collected from an indwelling intravenous canula in a superficial forearm vein.

Study visit day -1: Subjects will come fasting for this visit. Records of blood glucose concentrations monitored by fingerstick and CGM for the previous 14 days will be obtained to assess their glycemic control prior to liraglutide treatment (**this will serve as the baseline assessment of mean blood glucose for the study**). The subjects will have their 24 hour blood pressure measurements completed. Brachial reactivity will be assessed by measuring by flow mediated dilation (FMD). They will undergo a meal challenge test (described below) and a fat biopsy. 24 hr urine will be collected.

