Study Visit day 0: Subjects will come fasting for this visit. Each subject will be given one injection of Liraglutide 1.2 mg or placebo. A fructosamine and blood samples will be collected at baseline. Blood samples will be collected after the baseline at 30, 60, 120, 180, 240 and 300 minutes after the injection. (**This is being done to evaluate the acute effect of a single injection of Liraglutide on oxidative stress and inflammatory mediators, before any adjustments of insulin dose or effect of Liraglutide on blood glucose and weight is evident**). Subjects will be instructed by the study staff in the dosing and administration of the study medication. They will start Liraglutide injection at a dose of 0.6 mg per day or placebo injection on the following day. We will adjust the doses of basal and bolus insulin to eliminate low blood sugars(less than 70 mg/dl). At all subsequent visits insulin doses will be titrated to target blood sugars between 70-180 mg/dl at all times. Patients will return to the center after 7 days.

Study Visit week 1: Blood glucose concentrations will be reviewed. Insulin dose will be adjusted at the discretion of the study investigator to optimize blood sugar control as per

the targets mentioned above. Patients will be advised to increase the Liraglutide dose to 1.2 mg a day if they are able to tolerate the 0.6 mg dose. If they are experiencing mild nausea, subjects will continue with 0.6 mg daily for another 7 days. Those with severe nausea/vomiting will be dropped from the study. All other subjects will return in 7 days.

Study Visit week 2: Blood glucose concentrations will be reviewed. Insulin dose will be adjusted if needed. Subjects taking 0.6 mg dose and experiencing significant nausea will be dropped from the study. Subjects on 1.2 mg and experiencing significant nausea will decrease the dose to 0.6 mg and continue that dose for the duration of the study. Subjects on 1.2mg and experiencing mild nausea will continue on 1.2 mg for 2 more weeks. Subjects on Liraglutide 1.2mg daily without any gastro-intestinal side-effects will be asked to increase the dose to 1.8 mg daily. Study drug will be dispensed for additional 2 weeks.

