Study Visit week 26: Subjects will come fasting for this visit. Research labs, CBC, CMP, Lipids, HbA1c and fructosamine will be collected. Records of blood glucose concentrations monitored by finger-stick and CGM for the previous 14 days will be obtained to assess their glycemic control. They will undergo meal challenge test (described above) and a fat biopsy. 24 hr urine will be collected. FMD and 24hr blood pressure will be performed. After this visit, subjects will be discharged from the study.

Blood samples (collected in protease and DPP-IV inhibitors) will be appropriately processed and assayed for glucose, C-peptide, glucagon, GLP-1 and gastric inhibitory peptide (GIP) which is also called gastric insulinotropic peptide, Reactive oxygen species (ROS) generation, Thiobarbituric acid reducing substances (TBARS), urinary isoprostanate,

intranuclear nuclear factor kappa B (NFkB) binding, the expression and concentration of Toll like receptor-4 (TLR-4), tumor necrosis factor alpha (TNF α), Inhibitor kappa B (IkB α), Matrix metalloproteinase 9 (MMP-9), Suppressor of cytokine signaling-3 (SOCS-3), Protein kinase C (PKC β II), Phosphotyrosine phosphatase -1B (PTP-1B), Glycogen synthase kinase 3 beta (GSK-3 β), Inhibitor kappa kinase (IKK β), C-jun amino terminal kinase (JNK-1) and amount of Insulin receptor (IR- β) and p-IR β in MNC and plasma concentrations of C-reactive protein (CRP), Monocyte chemoattractant protein -1 (MCP-1), Plasminogen activator inhibitor -1 (PAI-1), TNF α and Regulated upon activation Normal T cell Expressed and Secreted (RANTES). Adipose tissue samples will be processed and analyzed for intranuclear NFkB binding, the expression and concentration of TLR-4, TNF α , IkB α , MMP-9, SOCS-3, PKC β II, PTP-1B, GSK-3 β , IKK β , JNK-1 and amount of IR- β and p-IR β .

Clinical and Laboratory Procedures

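### The detectable-C-peptide subset analysis is said to assess β-cell preservation, but its only post-treatment C-peptide is measured on drug, so it can speak only to on-treatment secretion

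*Combined protocol and SAP*

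**What the plan says.** The last item of the rationale list in section 3.1 of the combined protocol and SAP describes the subset: "An analysis in a subset of the study patients with detectable C-peptide will be carried out separately". It then states the purpose: "This will assess the effect of liraglutide in preserving β -cells". The same sentence adds a second purpose, how residual β-cell function affects the drug's action. Just before this, the item gives a related aim, "it will allow us to assess whether liraglutide can activate the dormant" β-cells.

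No cut-off, time point, size or test is given for the subset. The C-peptide data available to it are those of Aim 2.1 (section 1.2): "To compare the basal and postprandial glucagon and C-peptide concentrations following a test meal before and after 26 weeks of treatment with liraglutide". Hypothesis 2 (section 1.3) predicts that liraglutide "increases basal and postprandial C-peptide concentrations".

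On timing, section 10.1 says of the meal test: "Liraglutide will be injected only at week 26 (45 min prior to the meal"). The week 26 entry ends: "After this visit, subjects will be discharged from the study". Section 17.1 analyses C-peptide as change from baseline, between groups, by t-test or ANCOVA.

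**The concern.** Preservation means that β-cell function is better maintained at the end of treatment than it would have been without the drug. Showing it calls for a measure of function that the drug is not altering at the time. Here the baseline is drug-free and the only post-treatment measure is taken while the drug acts in one arm. A between-arm difference then mixes lasting function with whatever the drug does on the day.

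A positive result could be reported as preserved β-cells when it shows only stimulated secretion. A null result could be reported as no preservation when the drug had weakened the stimulus to secrete.

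**Working it through.** **1. Drug status at each C-peptide measurement**

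| Measurement | Place in the document | Drug status |
|---|---|---|
| Screening fasting C-peptide | 8.1, 10.1 | Off drug, both arms |
| Baseline meal test | 10.1, described under day -7 and listed again at day -1 | Off drug on either date; the first dose is on day 0 |
| Week 26 fasting sample | 10.1, week 26 | On drug: daily dosing, 24-hour action (3.1) |
| Week 26 meal samples | 10.1 | On drug, with an injection 45 min before the meal |
| After week 26 | 10.1 | None; patients are discharged |

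The pre-meal injection is not the root of the problem. With daily dosing and a 24-hour action, the week 26 samples would be on drug without it.

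**2. What the comparison estimates**

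Let p be true preservation and a the net effect of the drug on C-peptide on the test day, both in SDs of the change score. The between-arm difference in change estimates p + a. Placebo removes the effects of time and repeat testing from both arms. It does not remove a, because only one arm has active drug on board. Nothing in section 17.1 separates p from a.

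The sign of a is open. Stimulated secretion, as Hypothesis 2 and the dormant-cell aim allow, makes it positive. Lower post-meal glucose (Hypothesis 1) and delayed gastric emptying (Hypothesis 5) would reduce the stimulus and push it negative.

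**3. Illustration of size**

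The documents give no effect size, SD or subset size for C-peptide, so these inputs are assumptions: a from 0 to 1.0 SD, and n = 8, 12 or 20 per arm. For a two-sided t-test at 0.05, the chance of significance favouring liraglutide is

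P = 1 − F(t₀.₉₇₅; df = 2n − 2, δ), with δ = (p + a)·√(n/2),

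where F is the noncentral t distribution function with noncentrality δ.

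Worked case: p = 0, a = 0.5, n = 12. Then δ = 0.5 × √6 = 1.22, df = 22, t₀.₉₇₅ = 2.07, and P = 0.215.

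No preservation (p = 0):

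| n per arm | a = 0 | a = 0.3 | a = 0.5 | a = 0.8 | a = 1.0 |
|---|---|---|---|---|---|
| 8 | 2.5% | 8% | 15% | 32% | 46% |
| 12 | 2.5% | 10% | 22% | 47% | 65% |
| 20 | 2.5% | 15% | 34% | 69% | 87% |

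Masking, with assumed p = 0.8:

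| n per arm | a = 0 | a = −0.3 (p + a = 0.5) | a = −0.5 (p + a = 0.3) |
|---|---|---|---|
| 12 | 47% | 22% | 10% |
| 20 | 69% | 34% | 15% |

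The spread comes from the assumed inputs. It shows that the test responds to p + a and cannot tell the two apart. It does not estimate the bias in this trial.

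**The case against.** **Preservation is not a formal objective.** It appears in one background sentence. It is not among the aims (1.2), hypotheses (1.3) or endpoints (2.1), and section 17.1 does not mention the subset. Applying the t-test or ANCOVA of that section to the subset is an inference. This stands and limits the reach of the point. The sentence still commits to a separate analysis and says what it will show, and nothing later corrects it.

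**The documents contain evidence against an acute effect.** Section 3.1 reports that C-peptide did not change after short-term liraglutide in the pilot. That is the only evidence given, and it is why zero belongs in the range above. It does not settle the question, because the pilot patients had C-peptide below 0.10 nmol/l and are not shown to represent a subset chosen for detectable C-peptide.

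**The same data suit other stated aims.** This is right. Activation of dormant β-cells and Hypothesis 2 are on-drug questions, and the design can address them. Only the preservation reading fails.

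**Stronger readings.** A reader might infer that the analysis will report preservation falsely, or that the protocol itself expects an acute rise. The documents support neither. Hypothesis 2 names no mechanism, acute or lasting. The activation text says only that the question will be assessed. The pilot saw no short-term change, and the drug's effects on glucose and gastric emptying could push the result the other way. Nor should the 45-minute injection be read as the cause, since moving it would leave week 26 on drug.

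**Conclusion.** The stated inference does not follow from the design. The subset analysis can estimate the effect of liraglutide on C-peptide secretion during treatment. It cannot distinguish that from β-cell preservation, and it can mislead in either direction.

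This rests on the visit schedule, daily dosing and the protocol's own 24-hour duration of action. The size and sign of the bias are unknown. If the acute effect is zero, the false-positive rate favouring liraglutide stays at 2.5%. The upper figure of 87% needs an assumed 1.0 SD acute effect and 20 patients per arm, neither of which comes from the documents.

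The impact is confined to this unsized subset analysis. A reader might infer that the C-peptide secondary endpoint is undermined, but as a before-and-after comparison of concentrations under treatment it stands. The primary endpoint is untouched.

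**What to change.** In section 3.1, change the stated purpose of the subset analysis from preserving β-cells to on-treatment C-peptide secretion. Add a sentence that week 26 C-peptide is an on-drug measure from which β-cell preservation will not be concluded. The cost is a wording change, and the trial gives up a claim that its data cannot support.

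Two additions are optional context:

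- Report C-peptide by arm from the day 0 single-dose visit in the subset. Section 10.1 already schedules the draws: "Blood samples will be collected after the baseline at 30, 60, 120, 180, 240 and 300 minutes after the injection". The general assay list in 10.1 includes C-peptide without limiting it to particular visits, so this may need only clarification; otherwise it costs assays on samples already drawn. It is a rough guide to the acute component and not a correction. Day 0 is a fasting visit after one 1.2 mg injection with no meal, its stated purpose is oxidative stress and inflammation, and week 26 follows months of treatment at doses up to 1.8 mg.
- Show C-peptide beside the glucose measured at the same times, so that a weaker stimulus is visible. Both are already assayed. This remains an on-drug measure and does not isolate preservation.

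Neither option needs a new visit, blood draw or patient.

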4.0 Study Design

4.1 Describe and explain the study design (e.g. case-control, cross-sectional, ethnographic, experimental, interventional, longitudinal, observational).

Response: This investigation will be a prospective, randomized, double blind, placebo controlled parallel design study conducted in patients with type 1 diabetes. The study will be conducted at Diabetes-Endocrinology Center of WNY, affiliated to the State University of New York at Buffalo.

84 overweight or obese patients with type 1 diabetes on treatment with either continuous subcutaneous insulin infusion (CSII; also known as insulin pump) or multiple (four or more) injections of insulin per day will be included in the study. They will be randomized into 2 groups of 42 patients each. The patients will be randomized to daily subcutaneous injections of placebo or liraglutide. In view of the possibility of hypoglycemia and the side effect of nausea all patients will be started on 0.6 mg of liraglutide per day. The dose will then be titrated up to 1.8 mg.

5.0 Local Number of Subjects

5.1 Indicate the total number of subjects that will be enrolled or records that will be reviewed locally.

Response: 84

5.2 If applicable, indicate how many subjects you expect to screen to reach your target sample (i.e. your screen failure rate).

Response: 100-110. All screened and qualified patients will be enrolled and randomized up to 84 enrolled patients.

5.3 Justify the feasibility of recruiting the proposed number of eligible subjects within the anticipated recruitment period. For example, how many potential subjects do you have access to? What percentage of those potential subjects do you need to recruit?

Response: The Diabetes and Endocrinology Center of WNY is the largest Diabetes center in the WNY area, seeing between 60 and 100 type 1 diabetic patients every month. Therefore, majority of recruited patients are our clinic patients. We do recruit a few patients through advertisement and researchmatch.org. These sources will suffice to recruit the needed number to subjects.

6.0 Inclusion and Exclusion Criteria

6.1 Describe the criteria that define who will be **included** in your final study sample.

NOTE: This may be done in bullet point fashion.

Response:

- 1) Type 1 Diabetes on continuous subcutaneous insulin infusion (CSII; also known as insulin pump) or multiple (four or more) injections of insulin per day.
- 2) Using a continuous glucose monitoring device (CGM) or regularly measuring their blood sugars four times daily.
- 3) HbA1c of less than 10.0%.
- 4) Well versed with carbohydrate counting.
- 5) Age 18-80 years
- 6) $BMI \geq 25 \text{ kg/m}^2$
- 7) Age at diagnosis of type 1 diabetes should be <30 years.
- 8) Evidence of auto-immunity to beta cells (GAD-65 and islet cell antibody screen)

6.2 Describe the criteria that define who will be **excluded** from your final study sample.

NOTE: This may be done in bullet point fashion.

Response: 1) Type 1 diabetes for less than 6 months;
2) Coronary event or procedure (myocardial infarction, unstable angina, coronary artery bypass, surgery or coronary angioplasty) in the previous four weeks;
3) Hepatic disease (transaminase > 3 times normal) or cirrhosis;
4) Renal impairment (serum eGFR $<30 \text{ ml/min/1.73m}^2$);
5) HIV or Hepatitis B or C positive status;
6) Participation in any other concurrent clinical trial;
7) Any other life-threatening, non-cardiac disease;
8) Use of an investigational agent or therapeutic regimen within 30 days of study.
9) history of pancreatitis
10) pregnancy
11) inability to give informed consent
12) history of gastroparesis

- 13) history of medullary thyroid carcinoma or MEN 2 syndrome.
- 15) Use of any agent other than insulin for treatment of diabetes (metformin, pramlintide or thiazolidinediones;
- 16) painful gallstones;
- 17) alcoholism;
- 18) hypertriglyceridemia (>500 mg/dl)
- 19) History of pancreatitis

6.3 Indicate specifically whether you will include any of the following special populations in your study using the checkboxes below.

NOTE: Members of special populations may not be targeted for enrollment in your study unless you indicate this in your inclusion criteria.

Response: None of the below populations will be enrolled

- Adults unable to consent
- Individuals who are not yet adults (infants, children, teenagers)
- Pregnant women
- Prisoners

6.4 Indicate whether you will include non-English speaking individuals in your study. **Provide justification if you will exclude non-English speaking individuals.**

In order to meet one of the primary ethical principles of equitable selection of subjects, non-English speaking individuals may **not** be routinely excluded from research as a matter of convenience.

In cases where the research is of therapeutic intent or is designed to investigate areas that would necessarily require certain populations who may not speak English, the researcher is required to make efforts to recruit and include non-English speaking individuals. However, there are studies in which it would be reasonable to limit subjects to those who speak English. Some examples include pilot studies, small unfunded studies with validated instruments not available in other languages, studies with numerous questionnaires, and some non-therapeutic studies which offer no direct benefit.

Response: We have no non-English speaking patients in this population. We have patients that English is a second language, but they are able to read, write and understand it. This population is less than 10% of the total population.

